Comorbid Conditions	Hepatitis B and C co-infection, cardiovascular disease (y/n, type), psychiatric conditions (y/n, type), non-cancer pulmonary conditions (y/n, type), hepatic dysfunction, hematologic abnormalities, renal dysfunction, neurologic disorders, endocrine disorders (including thyroid disorders, and diabetes)
HIV Care	Current ART regimen, years of ART use, year of HIV diagnosis, history of opportunistic infections, recent HIV viral load and CD4+ T-cell count
Status of Cancer Diagnosis	New, primary or recurrent disease; current metastatic or locally advanced, inoperable cancer; history of malignancy diagnosed within 5 years / cancer currently in remission
Cancer Details	Cancer type, date cancer diagnosed, diagnosis methods (clinical, cytology, histology), pathology performed, date of pathology, staging, staging methods (clinical, radiographic, surgical), current ECOG Performance Status (PS), current laboratory (CBC) values, cancer treatment history (for metastatic tumors or disease in remission)
Cancer Treatment Plan	Planned treatment (e.g., chemotherapy versus radiation versus surgery versus antiretroviral therapy [ART] only versus best supportive care/watchful waiting), location of planned treatment, timeline of planned treatment (start date), if past diagnosis and treatment- end date, enrollment in clinical trial, and clinical trial details

Quality of Life/Survivorship	European Organization for Research and Treatment of Cancer Quality of Life Questionnaire (EORTC QLQ-C30: Global health status, physical functioning, role functioning, emotional functioning, cognitive functioning, social functioning, fatigue, nausea and vomiting, pain, dyspnea, insomnia, appetite loss, constipation, diarrhea, financial toxicity) and Supportive Care Needs Survey Short Form 34 (SCNS-SF34: psychological needs, health system and information needs, physical and daily living needs, patient care and support needs, sexuality needs)
------------------------------	---

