3.1 Eligibility Criteria

_____ 3.1.1 Participant can understand and is willing to sign a written informed consent document.

_____ 3.1.2 HIV positive. Documentation of HIV-1 infection by means of any one of the following:

- Documentation of an HIV diagnosis in the medical record by a licensed health care provider;
- Documentation of receipt of antiretroviral therapy (ART) (i.e., at least two different medications that do not constitute a prescription for pre-exposure prophylaxis [PrEP]) by a licensed health care provider. Documentation may be a record of an ART prescription in the medical record, a written prescription in the name of the participant for ART, or pill bottles for ART with a label showing the participant's name;
- HIV-1 RNA detection by a licensed HIV-1 RNA assay demonstrating >1000 RNA copies/mL;
- Any licensed HIV screening antibody and/or HIV antibody/antigen combination assay confirmed by a second licensed HIV assay such as a HIV-1 Western blot confirmation or HIV rapid multispot antibody differentiation assay.

Note: The term "licensed" refers to a kit that has been certified or licensed by an oversight body within the participating country and validated internally (e.g., U.S. FDA).

WHO (World Health Organization) and CDC (Centers for Disease Control and Prevention) guidelines mandate that confirmation of the initial test result must use a test that is different from the one used for the initial assessment. A reactive initial

rapid test should be confirmed by either another type of rapid assay, or an E/CIA that is based on a different antigen preparation and/or different test principle (e.g., indirect versus competitive), a Western blot, or a plasma HIV-1 RNA viral load.

- _____ 3.1.3 Patient was diagnosed with or treated for cancer within the last 5 years. Participants will qualify under one of three categories:
- New, primary or recurrent diagnosis –Considering or currently receiving cancer treatment
 - Metastatic or locally advanced cancer – This includes cases for which there are no current definitive therapy options for cure (i.e., inoperable) but may be considered for non-standard / non-curative therapies.
 - Prior diagnosis (within 5 years), in remission – Not currently on cancer treatment other than ART or maintenance therapy.
- _____ 3.1.4 Age \geq 18 years.
- _____ 3.1.5 Participant presents to an AMC domestic clinical trial site for either clinical care or research.

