8.2 Enrollment Data Collection

Following informed consent, additional, identifiable data will be collected, including:

- 8.2.1 Patient characteristics: Date of birth, biological sex, gender identity, race, ethnicity, height and weight
- 8.2.2 Sociodemographic: Socioeconomic status (e.g., ZIP code, housing status [homeless y/n, categories for frequency of housing insecurity]), health insurance (insured/uninsured, type if insured)
- 8.2.3 Health behaviors: Tobacco use (type, exposure [pack/day, years use]), illicit drug use (ever, type, years exposure), alcohol use (ever, exposure [drinks/week], years exposure)
- 8.2.4 Comorbid conditions: Hepatitis B and C co-infection, cardiovascular disease (y/n, type), psychiatric conditions (y/n, type), non-cancer pulmonary conditions (y/n, type), hepatic dysfunction, hematologic abnormalities, renal dysfunction, neurologic disorders, endocrine disorders (including thyroid disorders, and diabetes)
- 8.2.5 HIV care: Current ART regimen, years of ART use, year of HIV diagnosis, history of opportunistic infections, most recent HIV viral load and CD4+T-cell count relative to participant visit).

8.2.6 Status of cancer diagnosis (one of the following):

- New diagnosis, pre-treatment phase
- New diagnosis, treatment phase
- Prior diagnosis, in remission (within 5 years of initial diagnosis or treatment)
- Prior diagnosis, recurrent, pre-treatment phase
- Prior diagnosis, recurrent, treatment phase
- Prior diagnosis, recurrent, no treatment planned

8.2.7 For participants with a new diagnosis (pre-treatment or treatment), the following will be collected:

- Cancer type, date of cancer diagnosis, method of diagnosis (clinical, cytology, histology), type of pathology performed (Hematoxylin and Eosin, immunohistochemistry, other), date of pathology, staging, staging methods (clinical, radiographic, surgical), date(s) of staging, current ECOG Performance Status (PS), current laboratory values (this would include complete blood count, renal and liver function, electrolytes)
- Cancer treatment plan: Detailed planned or current treatment. This should encompass surgical interventions, radiotherapy, and chemotherapy (agent names), including dates of planned or current therapy, and whether cancer care is being received or will occur at the enrolling institution.

8.2.8 For participants with a prior diagnosis in remission, the following will be collected:

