8.3.1 Vital status

8.3.2 State of planned cancer therapy (initiated as planned versus delayed initiation, no initiation, or initiation of alternate therapy in place of planned therapy)

8.3.3 Optional QoL questionnaires as described in [Section 8.2.10](#):

- EORTC QLQ-C30
- SCNS-SF34

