10.3 Analysis of Secondary Endpoint and Analysis

The secondary endpoint is the proportion of participants eligible for AMC trials who are successfully enrolled.

For this calculation, the denominator will be computed based on PWH deemed eligible at each site, based only on AMC trials open at that respective site.

For participants with active disease, each participant's data will be evaluated to determine whether they meet minimal eligibility criteria for an AMC clinical trial open at

their respective domestic site, defined as meeting the following minimum eligibility criteria per the protocol:

- a. Cancer diagnosis including stage and histology
- b. Age range specified in the protocol for which the patient is being screened
- c. Indication for the study intervention (e.g., symptom, toxicity)

These data will be compared to the actual number of participants enrolled onto AMC trials open at each site to estimate the proportion of trial-eligible participants who enroll. For participants with a history of malignancy diagnosed within the past 5 years / cancer currently in remission, each patient's performance status and HIV metrics (CD4+ T-cell count and HIV viral load) will be evaluated to determine whether they meet general levels that are consistent with eligibility criteria for prior AMC clinical trials. To characterize participants who are eligible but not enrolled onto AMC trials, participant characteristics for eligible participants will be compared according to successful enrollment versus not using two-sample tests for continuous and categorical data (e.g., t-test, Wilcoxon rank sum test, chi-square test). Characteristics will include demographic features, clinical/cancer features, and optional QOL responses.

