EORTC QLQ-C30 subscale and overall scores will be used to describe participant symptom and health-related quality of life burden. SNSCS-SF34 scores will be used to categorize participants based on the degree to which their needs are met. Baseline EORTC QLQ-C30 and SCNS-SF34 scores will also be compared according to successful enrollment versus not using t-test or Wilcoxon rank sum tests depending on distribution of scores. These data may describe enrollment barriers previously unknown. For example, comorbidity burden, prior cancer treatment history, or self-reported quality of life at initial cancer presentation may be risk factors for elective participation. These analyses will provide preliminary data to inform evidence-based interventions aimed at increasing clinical trials participation among PWH at domestic AMC sites. To address minority and underserved populations, additional analyses will examine the interaction with race, ethnicity, socioeconomic status, and health insurance status to compare participant characteristics according to groups defined by enrollment status and these variables. Similarly, interactions with age, cancer type, treatment, and time since diagnosis will be investigated. Finally, these analyses will inform a multivariable logistic model that predicts successful trial outcome that includes dependent variables for participant characteristics; interactions with indicators of minority, socioeconomic status, and health insurance will be investigated in this model as well as with age, cancer type, treatment and time since diagnosis.

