To comply with investigator notification requirements for IND studies under 21 CFR 312.32 and 312.55, IND safety reports from all trials the AMC conducts and reports from external sponsors investigating the same agents are made available to all investigators upon receipt from the sponsor or its designee, either via the password-protected section of the AMC Operations web site (AMC trials subject to local IRB review only) or the CTSU website (U.S. trials subject to single IRB review/CTEP IND agents). The site clinical investigator responsible for the applicable AMC protocol(s) is responsible for reviewing any IND safety reports received and documenting submission to the IRB of record (if required by local policy) within the timeline defined by the Clinical Trials Monitoring Branch (CTMB) audit guidelines.

Procedures for monitoring trial progress and pharmacovigilance

For trials using AdvantageEDC or Advantage eClinical for clinical data entry, the AMC ODMC provides on demand tabular listings of all reported AEs and SAEs on a participant level to the protocol chair and co-chair(s) for review via the password-protected section of the AMC Operations web site, www.AIDScancer.org. For trials using OPEN and Medidata Rave for clinical data collection, data listing will be made available using that system. Summary reports of AEs by frequency and relationship to the investigational agent(s) are provided to all AMC investigators and their staff. It is the responsibility of each site to provide trial-specific AE listings to their respective IRB, if required by its policies. For blinded studies, the AE and SAE listings are reviewed and tabulated without treatment assignment.

Accrual summaries for each AMC trial are updated nightly on the password-protected section of the AMC web site. The progress of each AMC trial is reviewed regularly by the protocol chair and also by the appropriate Scientific Working Group (SWG) during scheduled conference calls (monthly SWG calls and as required, protocol-specific monitoring conference

calls). Summary accrual, summary AE, and individual SAE reports are provided to SWG leadership and protocol chairs to monitor participant safety during these monthly calls.

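### Section 10.3 reads quality-of-life and clinical differences as enrollment barriers without requiring that they were measured before trial enrollment, and gives no source or window for enrollment status

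*Combined protocol and SAP*

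**What the plan says.** **Endpoint (Section 10.3).** "The secondary endpoint is the proportion of participants eligible for AMC trials who are successfully enrolled". The denominator is the people judged eligible for AMC trials open at their own site. On the numerator the section says "These data will be compared to the actual number of participants enrolled onto AMC trials open at each site". It gives no data source, date or cut-off for enrollment status.

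**Barrier analysis (Section 10.3).** Demographic, clinical and optional quality-of-life features of eligible participants are compared by enrollment status, and then feed a multivariable logistic model. "Baseline EORTC QLQ-C30 and SCNS-SF34 scores will also be compared according to successful enrollment versus not". The section suggests that quality of life at first presentation with cancer, among other features, may influence who takes part.

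**Entry to AMC-115.** Section 3.1.3 admits patients who are considering treatment, are already on it, or are in remission. Section 3.1.5 reads: "Participant presents to an AMC domestic clinical trial site for either clinical care or research". Section 8.2.6 records the phase at entry, from "New diagnosis, pre-treatment phase" through treatment, remission and no treatment planned.

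**Where trial enrollment is recorded.** Table 2-A, under Cancer Treatment Plan, lists "enrollment in clinical trial, and clinical trial details". The itemised lists in Sections 8.2 and 8.3 do not repeat it. At Week 12, Section 8.3 has vital status, optional questionnaires and "State of planned cancer therapy (initiated as planned versus delayed initiation, no initiation, or initiation of alternate therapy in place of planned therapy". Appendix I, however, marks the Cancer Treatment Plan row at Week 12.

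**The concern.** A barrier has to come before the decision it is said to influence. The baseline of Section 10.3 is the AMC-115 enrollment visit, and nothing ties that visit to the date of a trial offer or trial enrollment. A participant already on an AMC trial can complete the QLQ-C30 and SCNS-SF34, and have performance status and laboratory values recorded, while on trial treatment. Any effect of that treatment would then appear as a difference between enrolled and not enrolled, and could be taken for a cause of enrollment.

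In the other direction, a participant who enters before treatment may join a trial after the visit. Unless status is captured again, that person counts as not enrolled.

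Section 10.3 says these results will inform interventions to raise participation, so the direction of an association matters. If enrollment dates are not collected, a later analysis may be unable to recover the order of events.

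**Working it through.** **1. No stated figure to reproduce.** Section 10.3 gives no expected enrollment rate, standard deviation, effect size or timing split. The plan's precision figures (Table 10-A) serve the primary objective and do not bear on this point.

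**2. Order of measurement.**
- Sections 3.1.3, 3.1.5 and 8.2.6 allow entry before or during treatment.
- Section 8.2.10 and Appendix I place the first questionnaires at that entry. Sections 8.2.5 and 8.2.11 take viral load and CD4 from around the AMC-115 visit, not from around the trial decision.
- Section 10.3 compares these measures by enrollment status with no condition that they came first.
- Section 10.3 plans interactions with treatment and time since diagnosis. Neither shows whether a given score came before enrollment.

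**3. Capture of enrollment status.**
- Section 2.2 says Table 2-A applies to everyone who consents, so status at entry is intended, although Section 8.2 does not itemise it.
- At Week 12, Appendix I read with Table 2-A implies the item. The Appendix I footnote then points to Section 8.3, which omits it. These passages conflict.
- Section 2.2 wants Week 12 quality-of-life change related to trial enrollment, which needs status at about that time.
- Under Section 8.4, participants not receiving treatment have no second visit. This can include recurrent disease with no treatment planned.

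**4. Illustration: measurement after enrollment. All inputs are assumptions.** No true difference; SD 25 points; 300 eligible participants with scores, of whom E = 36 or 72 enrolled; trial treatment lowers the score by e = 5 or 10 points; a share g of enrollees is measured after trial start.

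Spurious gap d = g × e. SE = 25 × √(1/E + 1/(300 − E)), which is 4.44 for E = 36 and 3.38 for E = 72. Chance of p < 0.05 in the direction of lower scores among enrollees = Φ(d/SE − 1.96); with no bias this is 2.5%.

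| g | e | d | Chance, E = 36 | Chance, E = 72 |
|---|---|---|---|---|
| 25% | 5 | 1.25 | 4.7% | 5.6% |
| 25% | 10 | 2.5 | 8.1% | 11.1% |
| 50% | 5 | 2.5 | 8.1% | 11.1% |
| 50% | 10 | 5.0 | 20.2% | 31.5% |
| 75% | 5 | 3.75 | 13.2% | 19.8% |
| 75% | 10 | 7.5 | 39.3% | 60.2% |

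If trial treatment raised scores instead, the gap would change sign.

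**5. Illustration: late enrollments missed. All inputs are assumptions.** With true proportion p and a share f of enrollees joining after the only capture of status, the observed proportion is p(1 − f). True enrollees make up pf / (1 − p(1 − f)) of the group labelled not enrolled.

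| p | f | Observed | Enrollees among the not enrolled |
|---|---|---|---|
| 10% | 10% | 9.0% | 0.01/0.91 = 1.1% |
| 10% | 50% | 5.0% | 0.05/0.95 = 5.3% |
| 20% | 10% | 18.0% | 0.02/0.82 = 2.4% |
| 20% | 50% | 10.0% | 0.10/0.90 = 11.1% |

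The proportion itself can be well off, but group differences are diluted only modestly. If no late enrollment is missed, this bias is zero.

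**The case against.** **The source may be sound.** Section 10.3 does not say that status comes from the AMC-115 form. The consortium holds enrollment data of its own: Appendix III states "Accrual summaries for each AMC trial are updated nightly". If such records were linked to participants, late enrollments need not be missed. This stands, so misclassification is a possibility and not a finding. But the plan describes no such link, and accrual summaries are not participant-level status.

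**Week 12 may already cover it.** A reader of Section 8.3 alone might infer that enrollment is not collected at Week 12. Appendix I with Table 2-A says otherwise. What stands is a conflict between passages, not an absent item.

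**The proportion is nested by definition.** A reader might infer from the numerator sentence that total site accrual is to be divided by AMC-115 eligibles. The documents do not support that. The sentence goes on to give its aim as the proportion of trial-eligible people who enroll, the endpoint is defined that way, and the next comparison splits eligible participants individually. The wording is loose and worth tightening, no more. Nor can both stronger readings hold together: one needs status from the visit, the other needs it from site accrual.

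**Partial safeguards exist.** Treatment phase and therapy dates are recorded, and the claims in Section 10.3 are hedged as preliminary. Phase does not replace an enrollment date, since a patient whose therapy is planned but not started may already be on a trial. An analysis limited to pre-treatment entrants would be possible, but none is planned.

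**Conclusion.** The concern holds for time-varying measures: quality of life, performance status, laboratory values, CD4 and viral load. As written, the barrier comparison can mix measurements taken before and after trial enrollment, and the planned interactions do not separate them. It does not hold for fixed characteristics such as race, ethnicity and sex, which trial treatment cannot change.

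Enrollment status lacks a stated source and window, and the passages on its capture conflict, so late enrollments may be missed. The documents do not show that they will be.

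The size of either bias cannot be computed from the documents. The illustrations run from negligible to substantial: a false gap of 1.25 to 7.5 points with about a 5% to 60% chance of a significant result, and a true 20% observed as 18% to 10%. Both rest wholly on the assumptions listed with them. The change is worth making because it is cheap and because the order of events may not be recoverable later.

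**What to change.** (a) Record AMC trial number and enrollment date at entry and at Week 12, and align Section 8.2, Section 8.3, Table 2-A and Appendix I.

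(b) State in Section 10.3 that the numerator is the AMC-115 eligible participants who enrolled on an open AMC trial within a stated window. Use AMC registration records for participants who have no Week 12 visit.

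(c) For time-varying measures, restrict the barrier comparisons and model terms to participants whose AMC-115 data precede any trial enrollment, and report the rest descriptively. Keep all eligible participants for fixed characteristics, so that the objective on minority and underserved groups loses no data.

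(d) Non-enrollees meet the condition in (c) automatically, even when already on non-trial treatment. Add a sensitivity analysis within the pre-treatment categories of Section 8.2.6.

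Cost: one or two form items, a registration check for participants without follow-up, and analysis-plan wording. The downside is fewer participants in the quality-of-life and performance-status comparisons.

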Fewer than 5% of U.S. adult cancer patients, and even fewer affected by both cancer and HIV/AIDS, enroll onto clinical trials. Research groups and government-sponsored organizations increasingly have focused on engaging communities to participate in cancer clinical trials. To broaden the understanding of characteristics of adults screened for, and those opting out of, NCI-sponsored cancer clinical trials, NCI Community Oncology Research Program (NCORP) developed a clinical trials screening tool (NCORP DCP-001). AIDS Malignancy Consortium (AMC) clinical trials share similar challenges to the NCI trials described in NCORP DCP-001 [2], so screening tools to identify consistent barriers to participation for people living with HIV (PWH), who have historically been under-represented in clinical trials, are urgently needed across the AMC. The AMC preliminarily examined patient-level characteristics and perceptions that influenced decision-making about trial participation for 67 patients diagnosed with anal cancer or high-grade anal intraepithelial neoplasia [3]. Of those 67 participants, most were male (92.5%) non-Hispanic white (89.5%) adults (48.3 years old on average); most learned about AMC clinical trials from a medical provider (98.5%); and most (73.1%) expressed little general knowledge about clinical trials. Participants recommended system-level changes to accelerate patient access to clinical trials. Participants further underscored the need to address knowledge barriers to clinical trial participation. This protocol will follow-up on these recommendations by proposing an AMC effort across all domestic sites to identify patient demographic (e.g., race/ethnicity), socioeconomic (e.g., homelessness/insurance status), and cancer-related (e.g., extent of disease) features associated with AMC clinical trial participation. This approach represents a large expansion beyond those preliminary data published from AMC-S006 by allowing enrollment across all domestic AMC sites, including all cancer types and AMC scientific working groups in data collection, and obtaining valuable information from not only participants who choose to enroll but, perhaps more importantly, from participants who present to AMC sites and are eligible for an open trial but who opt out of participation.

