2.2 Study Design and Rationale

Rationale: Collection of expanded patient demographics and clinical information to include socioeconomic status (SES), method of diagnoses, and engagement in recommended oncology care is one way to enhance our ability to evaluate both the full patient population served at AMC domestic sites and to identify factors influencing participation in AMC clinical trials. This includes features of both participants who are potentially eligible but elect not to screen for trials and participants who are screened but deemed ineligible. Understanding characteristics of those presenting for care at AMC sites is critical to inform the design of future AMC cancer prevention and treatment efforts and assessment of feasibility of proposed trials to make informed decisions for resource allocation. In addition, this information will be invaluable in informing survivorship programs for PWH and cancer.

Capturing patient health-related quality of life (QOL) experiences via patient-reported outcomes (PROs), is essential; thus, in 2020 the AMC formed the Patient Outcomes, Survivorship, and Engagement Committee (POSEC) to ensure that this data is documented in AMC trials using validated, culturally appropriate PRO tools that are of minimal burden to trial participants. Accordingly, this protocol will include an optional, brief PRO/QOL needs assessment that will allow for a better understanding of whether participant PRO/QOL features are potential barriers to clinical trial enrollment. This will serve as the first widespread use of QOL data across the AMC, both fulfilling the mission of POSEC and building a foundation for future, longitudinal survivorship efforts led by POSEC in the AMC.

In summary, anticipated outcomes of this observational protocol are as follows:

- Identify patient and clinical features associated with AMC clinical trial participation
- Capture a complete picture of cancer burden in PWH at domestic AMC sites to guide future clinical trial priorities
- Establish a robust population science framework for high-quality data collection across AMC sites
- Serve as the first protocol to build a foundation for future QOL-based and survivorship efforts across the domestic AMC

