8.1 Screening

All PWH who present for care at participating AMC clinical trial sites with a histologically confirmed diagnosis of cancer (within the past 5 years) will be tracked on a screening list. Eligibility will be assessed for each patient on the list, and if they are determined eligible, they will be approached to participate in AMC-115.

To determine the types of cancer cases that present to the clinical sites, all participants presenting at these sites have a minimum set of de-identified data collected. This minimal risk data collection will only include the participant's age, sex at birth, race/ethnicity, and type of cancer and will be performed prior to formal consent. Data collected during screening will be maintained separately from data on enrolled cases. This data will be compared to the total number of enrolled participants at each site to estimate the proportion of participants who consent to participate in this trial.

The protocol chair has established a set of IT logic codes that can be applied to electronic health record (EHR) systems to automate screening for "HIV status" among cancer patients. This is critical as it (1) makes the ascertainment of PWH and cancer uniform across participating domestic AMC sites and (2) reduces physician and study coordinator burden by leveraging the electronic medical record and automating the search. To ensure that this IT-based approach can be implemented across domestic AMC sites, the feasibility survey included a question specifically about the ability of sites to search their electronic medical record systems for HIV-specific disease codes.

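### Section 10.3 pools never-offered, screen-failed and declining patients as not enrolled, and the protocol specifies no data item that would separate them

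*Combined protocol and SAP*

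**What the plan says.** The aims distinguish several kinds of non-participant. Section 2.1 gives particular weight to patients who are "eligible for an open trial but who opt out of participation". The rationale in Section 2.2 extends this to "features of both participants who are potentially eligible but elect not to screen for trials and participants who are screened but deemed ineligible". The secondary objective (Section 1.2.1) is to understand accrual barriers at the level of the site and of the trial, with emphasis on minority and underserved patients.

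The analysis has two groups. Section 10.3 states: "The secondary endpoint is the proportion of participants eligible for AMC trials who are successfully enrolled". For participants with active disease, the data are used to "determine whether they meet minimal eligibility criteria for an AMC clinical trial open at" the participant's own site. Three criteria define this: diagnosis with stage and histology, age range, and indication for the intervention. After that, "participant characteristics for eligible participants will be compared according to successful enrollment versus not using two-sample tests". As an example of what may emerge, the section says that comorbidity burden, treatment history or "self-reported quality of life at initial cancer presentation may be risk factors for elective participation". The interaction analyses use the same enrollment status. So does the logistic model, if its successful trial outcome is read as enrollment, as the context suggests.

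On data capture, the one item about trial participation is in the treatment-plan row of Table 2-A: "enrollment in clinical trial, and clinical trial details". It is not defined further.

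**The concern.** A minimally eligible patient can remain unenrolled for three different reasons. If the trial was never offered, the barrier lies with the site or clinician. If the patient was screened and failed a criterion outside the three in Section 10.3, it lies with the trial. If the patient was offered the trial and declined, it lies with patient choice. Each calls for a different response from the consortium.

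Without a record of the step at which enrollment stopped, an association between non-enrollment and, say, insurance status or comorbidity can be reported but not placed. Comorbidity shows the problem well. Section 10.3 lists it among possible factors in elective participation, yet a trial that excludes patients for comorbidity would produce the same association with no patient choice involved. Section 10.3 intends the results to inform interventions to raise participation, so where the barrier lies matters. The gap is in data capture, and many participants have a single encounter, so later analysis can repair it only in part.

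**Working it through.** **1. Plan's own figure.** The plan gives no precision or effect figure for the secondary endpoint. Its only precision calculation, Table 10-A, serves the primary objective. Its eight prevalence intervals reproduce as p ± [1.96·√(p(1−p)/n) + 1/(2n)]; for example, 12.5% at n = 360 gives 8.9% to 16.1%. That table does not bear on this point.

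**2. Places where the missing item could be.**

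| Place | What it holds on trial participation |
|---|---|
| Table 2-A | Trial enrollment and undefined details |
| 8.1 and 12.1 (pre-consent list) | None: "age, sex at birth, race/ethnicity, and type of cancer and will be performed prior to formal consent" |
| 8.2.1 to 8.2.11 | No trial item. 8.2.9 asks the reason when no therapy is planned in recurrent disease |
| 2.2, follow-up paragraph | Reasons for planned therapy not starting, patient preference among them; about therapy, not a trial offer |
| 8.3.1 to 8.3.3 | Vital status, state of therapy, optional questionnaires; the reasons in 2.2 are not repeated |
| Appendix I | A treatment-plan row at enrollment and Week 12, without naming trial enrollment |

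No list names an offer, a screening attempt, a failed criterion or a refusal.

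**3. Effect of an unrecorded difference in offers.** All rates here are assumed; the documents give none. Enrollment probability = offer × acceptance × screen-pass, with acceptance 0.70 and screen-pass 0.50 in both groups.

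- Offer 60%: 0.60 × 0.70 × 0.50 = 0.210
- Offer 50%: 0.50 × 0.70 × 0.50 = 0.175
- Offer 30%: 0.30 × 0.70 × 0.50 = 0.105

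Odds ratio, 60% versus 50%: (0.210/0.790) ÷ (0.175/0.825) = 0.2658 ÷ 0.2121 = 1.25.

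Odds ratio, 60% versus 30%: 0.2658 ÷ (0.105/0.895) = 0.2658 ÷ 0.1173 = 2.27.

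Patient choice is identical in both comparisons.

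**4. Elective and non-elective causes can give the same pooled result.** Assume that a yes/no characteristic is present in 20% of enrollees. Let s be the share of decliners among the non-enrolled, so that pooled prevalence = s·p(decliners) + (1−s)·p(others). In scenario A, decliners match enrollees (20%) and the others have 40%. In scenario B, decliners have 40% and the others 20%. The table gives the odds ratio, not enrolled versus enrolled.

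| s | A: wholly non-elective | B: wholly elective |
|---|---|---|
| 100% | 1.00 | 2.67 |
| 75% | 1.33 | 2.15 |
| 50% | 1.71 | 1.71 |
| 25% | 2.15 | 1.33 |

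At s = 50% both scenarios give 30% versus 20%, so the odds ratio is (0.30/0.70) ÷ (0.20/0.80) = 1.71. The share s is itself unrecorded, so the enrolled/not-enrolled split cannot show which scenario applies.

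**The case against.** There is a fair case on the other side, and much of it limits the point.

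- **A reader might infer that this information will not be collected at all.** The documents do not support that. The case report forms and data entry guide are not part of them, Table 2-A is presented as a model, and its trial-details entry is undefined, so a suitable field could exist. What stands is that the protocol specifies none and Section 10.3 plans no analysis that would use one.
- **A reader might infer that the study will report non-offer and screen failure as refusal.** The text does not commit to this. Elective participation appears once in Section 10.3, as an example and with the word may. The nearby wording speaks of barriers not previously known and of preliminary data, and Section 1.2.1 names site and trial barriers. Nor does the plan say that later interventions would target patient attitudes.
- **A reader might infer that the secondary endpoint is invalid.** It is not. A difference in enrollment by race or insurance among minimally eligible participants is a real overall difference, whichever step produces it.
- **Some separation is possible with listed data.** Performance status, laboratory values, comorbidities, CD4 count and viral load could partly reconstruct screen failure, although Section 10.3 does not plan this for active disease. Patient preference in the follow-up text of Section 2.2 may catch some refusals where the planned therapy was a trial treatment, but only at Week 12. Neither source separates non-offer from refusal.
- **The size is assumed.** The odds ratio of 2.27 reflects a twofold gap in offers; a ten-point gap gives 1.25.

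**Conclusion.** The point holds as a gap between aim and specified data. Sections 2.1 and 2.2 undertake to describe patients who opt out, who elect not to be screened, and who are screened but ineligible. Section 10.3 merges them, and no specified item pulls them apart. The enrolled proportion and overall associations can be reported as planned; what cannot be supported is attributing them to site, trial criteria or patient choice.

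The documents do not allow the size to be estimated. Under the assumed acceptance and screen-pass rates, the enrollment odds ratio with no difference in patient choice runs from about 1.25 to about 2.27 as the lower offer rate falls from 50% to 30% against 60%. The lack of identifiability does not depend on those values. The conclusion assumes that the undefined trial-details entry in Table 2-A does not already hold these fields.

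This should be fixed. It concerns interpretation of the secondary objective in a non-interventional study and leaves the primary objective untouched.

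**What to change.** **Data.** Add a short block to Section 8.2, to Section 8.3 for participants with a Week 12 visit, and to Appendix I. Complete it for each AMC trial open at the site whose minimal criteria in Section 10.3 the participant meets:

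- offered: yes, no or not documented, with the reason for no offer if known;
- if offered: declined (main reason), screened and failed (criterion), or enrolled (date).

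If the case report forms already hold these fields, define the trial-details entry in Table 2-A accordingly and cite it in Section 10.3.

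**Analysis.** Keep the planned enrolled-versus-not comparison in Section 10.3. Add three steps: offered among eligible, accepted among offered, and passed among screened. Limit statements on elective participation to accepted versus declined among those offered a trial.

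**Cost.** This takes a few form fields, a paragraph in Section 10.3, a protocol amendment and a few minutes of coordinator time per participant concerned. Denominators shrink at each step. Some offers will be undocumented, and offers made after enrollment will be missed for participants without a Week 12 visit. The steps will describe only people who consent to AMC-115, because Section 12.1 allows no further data on those who do not.
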